## 4 TRIAL DESIGN

### 4.1 Overall Design

A Phase 2a, randomized, double-blind, vehicle-controlled, single-site, exploratory trial of delgocitinib cream 20 mg/g in subjects with FFA.

The trial will consist of 2 cohorts: Cohort 1 will include approximately 30 subjects with FFA and Cohort 2 will include approximately 5 healthy postmenopausal female subjects. Both cohorts can be conducted in parallel.

#### Cohort 1:

All subjects will read and sign an informed consent form (ICF) prior to any trial-related activities being performed. Subjects who fulfill all of the inclusion criteria and none of the exclusion criteria will be randomized into the trial. After a screening period of no more than 30 days (from Day -30 to Day -1), eligible subjects will be randomized (1:1) on Day 1 to apply delgocitinib cream 20 mg/g or vehicle cream BID for 12 weeks during the vehicle-controlled treatment period. All subjects who complete the vehicle-controlled treatment period will then continue into the OLE and apply delgocitinib cream 20 mg/g BID for 12 weeks. The OLE period will be followed by a 2-week safety follow-up period. For scheduled trial visits, subjects will come to the site on 9 occasions: screening, Day 1, Week 4, Week 8, Week 12, Week 16, Week 20, Week 24, and Week 26/early termination (ET).

On Day 1, a lesional target area on the scalp (eg, frontal, periauricular, or temporal area) that be treated with the IMP will be identified. To allow for the hair count/trichoscopy assessment and all samples collection (ie, skin biopsies, tape stripping, and skin swabs) the lesional target area should be approximately 3 cm x 6 cm (or equivalent). However, as tape strips can be collected from the same area where trichoscopy/hair counts is performed or can be collected adjacent/close to the lesional target area (refer to Section 8.3.2 for details), a smaller lesional target area may be acceptable. If needed, two small target areas (totalling approximately the same size) could also be selected to allow for skin samples collection and hair count/trichoscopy assessment. If two lesional target areas are selected, they should be of similar severity.

The following skin samples will be collected during the trial to assess molecular signature changes:

- Skin biopsies for transcriptomic and immunohistochemistry (IHC) analyses (n=3):
  - o *Day 1*: 2 skin biopsies (4-mm) will be collected prior to the first IMP application (1 from a lesional hair follicle within the target area and 1 from a non lesional hair follicle [eg, on the occipital scalp]).
  - o *Week 12*: 1 skin biopsy (4-mm) will be collected from a hair follicle within the lesional target area (outside the scar of previous biopsies).
- Skin swabs for microbiome analysis (n=3):
  - o *Day 1*: 2 skin microbiome samples will be collected prior to the first IMP application (1 from the target area [lesional skin] and 1 from an uninvolved occipital scalp area).

- *Week 12*: 1 skin microbiome sample will be collected at the same location of the lesional skin of the target area.
- Adhesive tape strips samples for transcriptomic analysis (n=3):
  - *Day 1*: skin tape strips will be collected prior to the first IMP application from lesional skin and from a nonlesional skin (eg, on the occipital scalp).
  - *Week 12*: skin tape strips will be collected at the same location of the lesional skin.

Note: Every effort should be made to collect tape strip samples in all subjects however, adhesive tape strip collection is optional and will be collected per investigator's judgement (based on available skin area on the scalp).

Safety will be assessed by collecting adverse events (AEs), recording vital signs, performing complete and brief physical examinations, and evaluating clinical laboratory results and local tolerability assessments (LTA).

Efficacy will be assessed using LPPAI, FFASS, evaluation of the perifollicular erythema and perifollicular scale, pruritus NRS, burning sensation NRS, pain NRS, and hair counts/trichoscopy (eg, number of hairs, hair diameter, and hair density). Hair line measurements (ie, lateral canthus [right and left] to hairline, lower glabellar crease to hair line, top of frontalis muscle to hair line, and mid brow to hair line [right and left]) will also be done.

Medical photographs of the lesional target area and the entire scalp (including the frontal hair line and right and left hair line areas) will be taken with the fotofinder device during the trial.

#### Cohort 2:

All subjects will read and sign an ICF prior to any trial-related activities being performed. Subjects who fulfill all of the inclusion criteria and none of the exclusion criteria will be accepted into the trial. After a screening period of no more than 30 days (from Day -30 to Day -1), eligible subjects will be asked to come at the site for skin samples collection. Screening and skin samples collection on Day 1 can be performed on the same day (if subjects do not have a washout period) or on two separate visits, at the investigator's discretion. No investigational product will be administered in Cohort 2. For scheduled trial visits, subjects will come to the site on up to 3 occasions: screening, Day 1, and optional follow-up visit.

The following skin samples will be collected:

- Skin biopsies (n=2):
  - *Day 1*: 2 skin biopsies (4-mm) that include hair follicles will be collected on healthy skin at similar matched areas of subjects with FFA (ie, 1 from frontal scalp area and 1 from occipital scalp area)
- Adhesive tape strips (n=1):
  - *Day 1*: skin tape strips will be collected on non-hair bearing healthy skin at a similar matched area of subjects with FFA (ie, on the forehead, as close as possible to the frontal scalp area).

- Skin swabs for microbiome analysis (n=2):
  - o *Day 1*: 2 skin microbiome samples will be collected on healthy skin at similar matched areas of subjects with FFA (ie, 1 from frontal scalp area and 1 from occipital scalp area).

For Cohort 2 only, safety will be assessed by review of any procedural complications and changes in health observed after skin samples collection.

No interim analysis is planned in this trial.

## 4.2 Scientific Rationale for Trial Design

This is an exploratory trial to interrogate the effect of delgocitinib cream 20 mg/g on the molecular signature of active FFA. Frontal fibrosing alopecia demonstrated significant upregulation of T helper 1/IFN (IFN- $\gamma$ , CXCL9/CXCL10), the JAK-STAT pathway (STAT1, JAK3) and fibrosis-related products (vimentin, fibronectin). Delgocitinib is a novel pan- JAK inhibitor. It is hypothesized that delgocitinib cream 20 mg/g will reduce INF- $\gamma$  driven inflammation in subjects with FFA. The proposed design is considered appropriate for assessing the molecular signature changes, the safety, as well as preliminary efficacy of delgocitinib cream 20 mg/g in subjects with FFA.

In this Phase 2a trial, the vehicle-controlled treatment period will be randomized to ensure random allocation of subjects to treatment arms to reduce bias. Because efficacy assessments of FFA have a high degree of subjectivity, the trial will be double-blinded. The highest degree of patient and assessor blinding should be sought to achieve credible inference. It is also important to have a vehicle control in the Phase 2a trial to control for confounding factors, such as potential investigator bias, and to ensure that the statistical procedures can be appropriately applied. After completion of the vehicle-controlled treatment period, all subjects will have the opportunity to continue into the OLE and to receive the active drug for a period of 12 weeks.

Inclusion of 5 healthy postmenopausal female subjects to collect skin samples will allow comparison of the molecular and cellular fingerprint to that of subjects with FFA.

## 4.3 Justification for Dose

The justification for the delgocitinib dose is based on the findings from the Phase 2b trial in subjects with AD. Delgocitinib cream was tested at 4 different strengths (1, 3, 8, and 20 mg/g) BID for up to 8 weeks in subjects with AD. A statistically significant dose-response was established for the primary endpoint (change in Eczema Area and Severity Index [EASI] from baseline to Week 8), and the secondary endpoints (Validated Investigator Global Assessment for Atopic Dermatitis treatment success [VIGA-AD TS] at Week 8 and EASI75 [a 75% reduction in EASI score] at Week 8). The highest treatment effect (compared to cream vehicle) was seen with delgocitinib cream 20 mg/g.

#### 4.4 End of Trial Definition

A subject is considered to have completed the trial if he or she has completed all phases of the trial, including the last visit or the last scheduled procedure shown in the Schedule of Events, [Table 1](#) (for Cohort 1) and [Table 2](#) (for Cohort 2).

The end of the trial is defined as completion of the last visit or procedure shown in the schedule of event for the last enrolled subject in Cohort 1 and Cohort 2.

## 5 TRIAL POPULATION

### 5.1 Inclusion Criteria

In order to be eligible to participate in this trial, a subject must meet all of the following criteria, either at the screening and Day 1 visits or only at one of the specified visits (screening or Day 1) as noted in the criterion:

#### Inclusion criteria for all subjects:

1. Subject is willing to participate and is capable of giving informed consent. Note: Consent must be obtained prior to any trial-related procedures.
2. Subjects must be willing to comply with all trial procedures and must be available for the duration of the trial.

#### Inclusion criteria for Cohort 1 only (subjects with FFA):

3. Male or female subject aged 18 years of age or older at the time of consent.
4. Female subject of childbearing potential has had a negative serum pregnancy test at screening and negative urine pregnancy test at Day 1.
5. Subject has clinically confirmed diagnosis of FFA based on investigator's judgment.
6. Subject has a target area with a perifollicular erythema score  $\geq 2$  and a perifollicular scale score  $\geq 2$  at Screening and Day 1.
7. For subject who uses make-up, moisturizers, creams, lotions, cleansers, and/or sunscreens on the face, subject has used the same product brands/types for a minimum period of 4 weeks prior to Day 1, agrees not to change brand/type or frequency of use throughout the trial, agrees not to apply those products on the treated area during the trial, and agrees not to use make-up, moisturizers, creams, lotions, cleansers, and/or sunscreens on the face on the clinic visit days before the visit.

8. Subject is willing to maintain a consistent hair style and hair style regimen, including shampoo and hair products (including hair dye, process, and timing to hair appointments), and to refrain from weaves or extensions throughout the course of the trial and for 4 weeks prior to Day 1.

Note: Hair dying and shaving of scalp is allowed during the trial but not within 48 hours prior to a trial visit

9. For female subject of childbearing potential involved in any sexual intercourse that could lead to pregnancy: the subject must agree to use an effective contraceptive method from at least 4 weeks prior to Day 1 until at least 4 weeks after the last IMP application. Effective contraceptive methods include hormonal contraceptives (eg, combined oral contraceptive, progesterone-only hormonal contraception [associated with or without inhibition of ovulation as the primary mode of action], patch, vaginal ring, injectable, or implant), intrauterine devices or intrauterine systems, vasectomized partner(s) (provided his vasectomy was performed  $\geq 4$  months prior to Screening), tubal ligation or a barrier method of contraception (eg, male condom, female condom, cervical cap, diaphragm, contraceptive sponge) in conjunction with spermicide.

Note: Subjects must have been on a stable dose of hormonal contraceptives for at least 4 weeks before Day 1.

Note: The above list of contraceptive methods does not apply to subjects who are abstinent for at least 4 weeks before Day 1 and will continue to be abstinent from penile-vaginal intercourse throughout the trial. The reliability of sexual abstinence needs to be evaluated in relation to the duration of the clinical trial and the preferred and usual lifestyle of the subject. Periodic abstinence (calendar, symptothermal, post-ovulation methods) is not acceptable.

Note: A female subject of nonchildbearing potential is defined as follows:

- Female subject who has had surgical sterilization (hysterectomy, bilateral oophorectomy, or bilateral salpingectomy)
- Female subject who has had a cessation of menses for at least 12 months prior to the screening visit without an alternative medical cause

Inclusion criteria for Cohort 2 only (healthy subjects):

10. Female subject aged 45 years of age or older at the time of consent.
11. Female is postmenopausal as defined below:
  - Female subject who has had surgical sterilization (hysterectomy, bilateral oophorectomy, or bilateral salpingectomy)
  - Female subject who has had a cessation of menses for at least 12 months prior to the screening visit without an alternative medical cause.
12. Subject is in good general health, according to the investigator's judgment based on vital signs, medical history, and brief physical examination.

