# 1 PROTOCOL SUMMARY

## 1.1 Synopsis

Name of Sponsor/Company:	Name of Investigational Product:	Name of Active Ingredient:
LEO Pharma A/S	Delgocitinib cream 20 mg/g	Delgocitinib
Title of Trial:		
A Phase 2a, Randomized, Double-Blind, Vehicle-Controlled, Single Site, Exploratory Trial to Assess the Effect of Delgocitinib Cream 20 mg/g on the Molecular Signature, Safety, and Efficacy in Adults with Frontal Fibrosing Alopecia		
Phase of Development:		
Phase 2a		
Trial Site:		
This trial will be conducted at 1 site located in the United States PPD [REDACTED] Boston, MA).		
Number of Subjects (planned):		

• Cohort 1

- Approximately 30 subjects with frontal fibrosing alopecia (FFA) will be randomized in this cohort.

• Cohort 2

- Approximately 5 healthy postmenopausal female subjects will be included in this cohort.

		
Duration of Trial:		

• Cohort 1

- The maximum trial duration per subject is approximately 30 weeks, including up to 30 days for the screening period, 12 weeks for the vehicle-controlled treatment period, 12 weeks for the open-label extension (OLE), and approximately 2 weeks for the safety follow-up period.

• Cohort 2

- The maximum trial duration per subject is approximately 6 weeks, including up to 30 days for the screening period, 1 day for the skin samples collection, and up to 14 days for the optional follow-up period.

		
Investigational Medicinal Product, Dosage, and Mode of Administration:		
Delgocitinib cream 20 mg/g and matching vehicle (delgocitinib cream vehicle).		

• Cohort 1

- Subjects will be randomized in a 1:1 ratio on Day 1 to apply delgocitinib cream 20 mg/g or vehicle cream twice daily (BID) for 12 weeks during the vehicle-controlled treatment period.

		

Name of Sponsor/Company:	Name of Investigational Product:	Name of Active Ingredient:
LEO Pharma A/S	Delgocitinib cream 20 mg/g	Delgocitinib

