
7. For subject who uses make-up, moisturizers, creams, lotions, cleansers, and/or sunscreens on the face, subject has used the same product brands/types for a minimum period of 4 weeks prior to Day 1, agrees not to change brand/type or frequency of use throughout the trial, agrees not to apply those products on the treated area during the trial, and agrees not to use make-up, moisturizers, creams, lotions, cleansers, and/or sunscreens on the face on the clinic visit days before the visit.
 
8. Subject is willing to maintain a consistent hair style and hair style regimen, including shampoo and hair products (including hair dye, process, and timing to hair appointments), and to refrain from weaves or extensions throughout the course of the trial and for 4 weeks prior to Day 1.
 
Note: Hair dying and shaving of scalp is allowed during the trial but not within 48 hours prior to a trial visit.
 
9. For female subject of childbearing potential involved in any sexual intercourse that could lead to pregnancy: the subject must agree to use an effective contraceptive method from at least 4 weeks prior to Day 1 until at least 4 weeks after the last IMP application. Effective contraceptive methods include hormonal contraceptives (eg, combined oral contraceptive, progestin-only hormonal contraception [associated with or without inhibition of ovulation as the primary mode of action], patch, vaginal ring, injectable, or implant), intrauterine devices or intrauterine systems, vasectomized partner(s) (provided his vasectomy was performed <math>\geq 4</math> months prior to Screening), tubal ligation or a barrier method of contraception (eg, male condom, female condom, cervical cap, diaphragm, contraceptive sponge) in conjunction with spermicide.
 
Note: Subjects must have been on a stable dose of hormonal contraceptives for at least 4 weeks before Day 1.
 
Note: The above list of contraceptive methods does not apply to subjects who are abstinent for at least 4 weeks before Day 1 and will continue to be abstinent from penile-vaginal intercourse throughout the trial. The reliability of sexual abstinence needs to be evaluated in relation to the duration of the clinical trial and the preferred and usual lifestyle of the subject. Periodic abstinence (calendar, symptothermal, post-ovulation methods) is not acceptable.
 
Note: A female subject of nonchildbearing potential is defined as follows:
 

– Female subject who has had surgical sterilization (hysterectomy, bilateral oophorectomy, or bilateral salpingectomy)

– Female subject who has had a cessation of menses for at least 12 months prior to the screening visit without an alternative medical cause

 
Inclusion criteria for Cohort 2 only (healthy subjects):
 
10. Female subject aged 45 years of age or older at the time of consent.
 
11. Female is postmenopausal as defined below:
 

– Female subject who has had surgical sterilization (hysterectomy, bilateral oophorectomy, or bilateral salpingectomy)

– Female subject who has had a cessation of menses for at least 12 months prior to the screening visit without an alternative medical cause.

 
12. Subject is in good general health, according to the investigator's judgment based on vital signs, medical history, and brief physical examination.
		

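### The abstinence note to Inclusion Criterion 9 ends with the trial, nominally 15 days after the last application, while the criterion itself runs to at least 4 weeks

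*Combined protocol and SAP*

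**What the plan says.** Criterion 9 in Section 5.1 opens with its condition, "For female subject of childbearing potential involved in any sexual intercourse that could lead to pregnancy", and requires an effective method from at least 4 weeks before Day 1 "until at least 4 weeks after the last IMP application".

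A note under the criterion makes an exception. In the synopsis it begins "The above list of contraceptive methods does not apply to subjects who are abstinent for at least 4 weeks before Day 1" and goes on to require that the subject "will continue to be abstinent from penile-vaginal intercourse throughout the trial". Section 5.1 has the same wording. The note adds that the reliability of abstinence "needs to be evaluated in relation to the duration of the clinical trial and the preferred and usual lifestyle of the subject", and it rejects periodic abstinence.

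Three other places fix the dates:

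- Section 6.1 and Table 1 (footnote g) put the last application on the evening before the Week 24 visit.
- Table 1 puts the last scheduled visit at Week 26, with windows of ±4 days at both Week 24 and Week 26.
- Section 4.4 defines completion for a subject ("A subject is considered to have completed the trial if he or she has completed all phases of the trial, including the last visit") and, separately, the end of the whole trial, which is set by the last enrolled subject.

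**The concern.** The note takes over the criterion's start, 4 weeks before Day 1, but not its end. The criterion is tied to the last application and the note to the trial. The protocol gives no reason for a shorter period for abstinent women, so this looks like a drafting slip.

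The purpose is to prevent exposure of a pregnancy, and the sponsor has set 4 weeks after the last application as its standard. As written, a woman relying on abstinence can meet the note in full and still be released before that standard is reached, while a woman with the same exposure who uses contraception is not. Sites need one end date to give to both.

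**Working it through.** **Inputs**

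- Required interval after the last application: at least 4 weeks = 28 days (Criterion 9).
- Last application: Week 24 visit minus 1 day (Section 6.1; Table 1, footnote g).
- Week 24 to Week 26: 14 days (Section 4.1; Table 1).
- Windows: ±4 days at each of the two visits (Table 1).

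**The plan's own figure.** The synopsis says: "The maximum trial duration per subject is approximately 30 weeks". Its parts give 30/7 + 12 + 12 + 2 = 30.3 weeks, which agrees. The synopsis therefore uses the trial as a per-subject period that ends at Week 26, in line with the completion definition in Section 4.4.

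**Per-subject reading, completer**

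- Interval from last application to Week 26: 14 + 1 = 15 days.
- Shortfall: 28 − 15 = 13 days.
- With windows, the gap between the visits is 14 − 8 = 6 to 14 + 8 = 22 days, so the interval is 7 to 23 days.
- Shortfall with windows: 28 − 23 = 5 to 28 − 7 = 21 days. No in-window combination reaches 28.

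**Whole-trial reading**

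- Day 28 after the last application is 28 − 1 = 27 days after the subject's own Week 24 visit, or 27 − 14 = 13 days after her nominal Week 26 visit.
- She is covered only if the trial's last visit falls on or after that day. Cohort 1 subjects who finish later than that are short. This includes the last one enrolled, unless a Cohort 2 visit comes that much later.

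**Early withdrawal.** The documents do not say when the trial ends for a subject who stops early. If it ends at the early termination visit (an assumption), the shortfall is 28 minus the days from last application to that visit. Section 7.1 sets no interval for the visit.

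**Does another rule close the gap?**

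- Exclusion Criterion 1 covers women planning pregnancy, but only within the trial.
- The last scheduled urine pregnancy test is at Week 26 (Table 1).
- Section 8.5.8 asks for notification of pregnancies up to 4 weeks after the end of the trial. If that end is her own Week 26 visit, notification runs to 15 + 28 = 43 days after the last application (35 to 51 with windows). That is reporting and does not require abstinence or contraception.

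**The case against.** The strongest counter-argument is that the note waives only the list of methods, and that the criterion's main clause remains in force. A woman who resumed intercourse on day 20 after her last application would then come back under that clause while its 4 weeks were still running. This reading is possible, but the text does not state it, and the note grants its waiver on the shorter condition. The lead-in to Section 5.1 says "a subject must meet all of the following criteria, either at the screening and Day 1 visits" or at one specified visit, so the commitment is the one given at entry, and the commitment the note asks for ends with the trial. It is fair to reply that contraception users also give theirs at entry and have no scheduled visit after Week 26. The difference is that theirs names the 4 weeks.

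It can also be said that the size depends on which end of trial is meant. That is true, and on the whole-trial reading women who finish early are covered. A protection period should not depend on other subjects' visit dates, however, and late finishers remain short.

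The practical objections stand. Harm would need a woman whose abstinence was judged reliable against her usual lifestyle to resume intercourse within about two weeks of Week 26 without contraception. Systemic exposure has been low (Section 2.2.1), and the documents give no data showing that 15 days is less safe than 28. These points limit the weight of the issue but do not reconcile the two end dates. The consent form was not available for this review, so what subjects are told about duration cannot be checked.

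**Conclusion.** The concern holds. The abstinence note ends earlier than the criterion it belongs to. For a completer on the per-subject reading the gap is nominally 13 days, and 5 to 21 days across the visit windows. The whole-trial reading removes it only for subjects whose Week 26 visit falls early enough before the trial's last visit. The early-withdrawal figure rests on the assumption that her trial ends at the early termination visit.

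The weight is low. About 30 subjects are randomized, and FFA is most common in postmenopausal women (Section 2.1.1). Cohort 1 does admit women from age 18, so the rule can apply. The number of abstinent women of childbearing potential is not given and may be zero. The primary and other endpoints, the sample size and the analyses are unaffected.

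**What to change.** In the abstinence note, in both Section 5.1 and the synopsis, replace the reference to the trial's length with the end point of the main clause, "until at least 4 weeks after the last IMP application", and add that this also applies after early withdrawal. Anchoring to the last application removes the dependence on which end of trial is meant and covers early stoppers. The sentence on reliability could be aligned in the same edit, but the correction does not depend on it.

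The cost is one phrase in two places, with no added visits, tests or data. As a protocol change it needs IRB/REB approval before use (Statement of Compliance), and the consent form should be checked for the same end date.
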